## 5.2 Exclusion Criteria

Volunteers will be excluded from study participation for any of the following:

1. History or presence of clinically significant cardiovascular, pulmonary, hepatic, renal, hematological, gastrointestinal, endocrine, immunologic, dermatologic, neurological (including epilepsy), oncologic, or psychiatric disease or any other condition that, in the opinion of the Investigator, would jeopardize the safety of the subject or the validity of the study results.
2. Any abnormality on neurologic exam.
3. History of any illness that, in the opinion of the Investigator, might confound the results of the study or pose an additional risk to the subject by their participation in the study.
4. Surgery within the past 90 days prior to dosing as determined by the Investigator to be clinically relevant, or any history of cholecystectomy.
5. History or presence of alcoholism or drug abuse within the past 2 years as determined by the Investigator to be clinically relevant.
6. History of sensitivity or contraindication to use of linezolid, tedizolid, or any study investigational products.
7. Participation in another clinical trial within 30 days prior to dosing.
8. Female subjects who are pregnant or lactating.
9. Positive result on a urine drug/alcohol/cotinine screen at Baseline or check-in.
10. Seated blood pressure is less than 90/40 mmHg or greater than 140/90 mmHg at screening. Out-of-range vital signs may be repeated once for confirmation.
11. Seated heart rate is lower than 40 bpm or higher than 99 bpm at screening. Out-of-range vital signs may be repeated once for confirmation.
12. Any clinically significant ECG abnormality at Screening (as deemed by decision of the Investigator and the Sponsor's Medical Monitor).

*NOTE: The following may be considered not clinically significant without consulting the Sponsor's Medical Monitor:*

- Mild first-degree A-V block (P-R interval <0.23 sec)
- Right or left axis deviation

- Incomplete right bundle branch block
- Isolated left anterior fascicular block (left anterior hemiblock) in younger athletic subjects
- Early repolarization
- Tall T waves
- RSR in V1/V2 consistent with right ventricular conduction delay (with acceptable QRS)
- Sinus rhythm or sinus bradycardia with sinus arrhythmia
- Minimal or moderate voltage criteria for left ventricular hypertrophy (LVH).

13. QTcF interval >450 msec for males or >470 msec for females at screening, Day -1, or Day 1 (predose), or history of prolonged QT syndrome. For the triplicate ECGs taken at screening and on Day -1, the average QTcF interval of the three ECG recordings will be used to determine qualification.
14. Family history of long-QT syndrome or sudden death without a preceding diagnosis of a condition that could be causative of sudden death (such as known coronary artery disease, congestive heart failure, or terminal cancer).
15. History of any of the following:
  - Serotonin syndrome
  - Seizures or seizure disorders, other than childhood febrile seizures
  - Brain surgery
  - History of head injury in the last 5 years
  - Any serious disorder of the nervous system particularly one that may lower the seizure threshold.
16. Lactose intolerant.

#### Specific Treatments

17. Use of any prescription medication within 14 days prior to dosing.
18. Use of any of the following medications within 30 days before the first dose of study drug or during the study drug treatment period: monoamine oxidase (MAO) inhibitors (phenelzine, tranylcypromine), tricyclic antidepressants (amitriptyline, nortriptyline, protriptyline, doxepin, amoxapine, etc.), antipsychotics such as chlorpromazine and buspirone, serotonin re-uptake inhibitors (fluoxetine, paroxetine, sertraline, etc.), bupropion, agents known to prolong the QTc interval

(erythromycin, clarithromycin, astemizole, type Ia [quinidine, procainamide, disopyramide] and III [amiodarone, sotalol] anti-arrhythmics, carbamazepine, sulfonylureas, and meperidine).

19. Use of any over-the-counter (OTC) medication, including herbal products and vitamins, within 7 days prior to dosing, except acetaminophen. Up to 3 grams per day of acetaminophen is allowed at the discretion of the Investigator prior to dosing.
20. Use of any drugs or substances known to be significant inhibitors of cytochrome P450 (CYP) enzymes and/or significant inhibitors or substrates of P-glycoprotein (P-gp) and/or organic anion transporting polypeptides (OATP) within 14 days prior to the first dose of study drug.
21. Use of any drugs or substances known to be inducers of CYP enzymes and/or Pgp, including St. John's Wort, within 30 days prior to the first dose of study drug.
22. Use of any drugs or substance known to lower the seizure threshold.

#### Specific Laboratory Abnormalities

23. Serum magnesium, potassium, or calcium laboratory values outside of the normal range at screening. If exclusionary lab criteria are met, values may be confirmed by repeat evaluation.
24. Positive results at screening for human immunodeficiency virus (HIV), hepatitis B surface antigen (HBsAg), or hepatitis C antibodies (HCV).
25. ALT or AST greater than ULN.

### **5.3 Medication and Activity Restrictions**

1. Subject must not donate blood from 56 days or plasma from 7 days prior to the first dose of study medication until after the follow-up phone call. It is recommended that blood/plasma donations not be made for at least 30 days after discharge from the clinic.
2. Subject must not use tobacco- or nicotine-containing products (including smoking cessation products) from 6 months prior to the first dose of study medication until after the follow-up phone call.
3. Subjects must not consume alcohol from 72 hours prior to the first dose of study medication until after the follow-up phone call.
4. Subject must not consume beverages or foods that contain grapefruit or Mandarin oranges from 10 days before the first dose of study medication, or poppy seeds, broccoli, Brussels sprouts, pomegranate, star fruit, char grilled meat, or caffeine/xanthine from 48 hours before the first dose of study medication, until

after discharge from the clinic. Subjects will be instructed not to consume any of the above products; however, allowance for an isolated single incidental consumption may be evaluated and approved by the study Investigator based on the potential for interaction with the study drug.

5. Subject should avoid large quantities of foods or beverages with high tyramine content 48 hours prior to the first dose of study medication until discharge from the clinic. Quantities of tyramine consumed should be less than 100 mg per meal. Foods high in tyramine content include those that may have undergone protein changes by aging, fermentation, pickling, or smoking to improve flavor, such as aged cheeses (0 to 15 mg tyramine per ounce); fermented or air-dried meats (0.1 to 8 mg tyramine per ounce); sauerkraut (8 mg tyramine per 8 ounces); and soy sauce (5 mg tyramine per 1 teaspoon). The tyramine content of any protein rich food may be increased if stored for long periods or improperly refrigerated.
6. Subject must not engage in strenuous exercise from 48 hours prior to the first dose of study medication until after discharge from the clinic.
7. Subject must be willing to remove any artificial nails (e.g., acrylic, gel) or fingernail polish and not use such products for the duration of the study.
8. Subject must not take any adrenergic/serotonergic agonists, such as pseudoephedrine and phenylpropanolamine (frequently found in cold and cough remedies), within 7 days before the first dose of study drug or during the study drug treatment period.

#### 5.4 Screening

The informed consent documents will be discussed with each potential participant, and each individual will sign an informed consent document for the study prior to any study-specific procedures being performed.

Each potential study participant will have the following assessments by the Investigator or designee within 28 days prior to study start:

- Demographic data, including sex, age, race, ethnicity, body weight (kg), height (cm), BMI (kg/m^2), and smoking habits.
- Medical history
- Serology tests for HIV, hepatitis B and C
- Clinical laboratory tests (hematology, chemistry, and urinalysis)
- Coagulation test
- Serum pregnancy (all female subjects)
- FSH test (female subjects claiming post-menopausal status)
- Urine test for drugs of abuse, alcohol, and cotinine

- Physical and neurological examinations
- Triplicate 12-lead safety ECGs
- Vital signs (blood pressure, pulse rate, respiration rate, temperature, and pulse oximetry)
- Concomitant medication review

Only medically healthy subjects with clinically acceptable laboratory profiles and ECGs within the defined parameters who fulfill all other inclusion criteria and meet none of the exclusion criteria outlined in the previous sections will be enrolled in the study.

Subjects will be assigned numbers in an ascending order, based on successful completion of the screening process.

## **6 STUDY PROCEDURES**

### **6.1 Subject Assignment**

Thirty-six (36) subjects are planned to be enrolled in the study, 12 subjects per cohort. Additional subjects may be enrolled if deemed appropriate by the Sponsor to repeat a dose level or to study another dose level. The number of subjects for each cohort is expected to provide sufficient safety and tolerability data to evaluate whether escalation to the next dose level is warranted. This study has not been formally powered.

Each subject will receive an assigned treatment (active or placebo) based on the randomization schedule prepared by the unblinded statistician. The unblinded pharmacy staff will ensure compliance with the randomization schedule.

### **6.2 Blinding**

All subjects and clinical staff (except for the unblinded pharmacy staff) will be blinded to treatment. An unblinded pharmacy staff will be required at the Clinical Site to comply with the study's randomization and blinding requirements. At the Clinical Site, prior to study initiation, the Principal Investigator will be responsible for designating a qualified pharmacy staff to serve as the unblinded pharmacy staff in the study. Unblinded pharmacy staff may dose subjects but may not participate in any subject assessments.

Throughout the study, the designated unblinded pharmacy staff will be responsible for all drug accountability issues, including preparing, labeling, dispensing, and dosing study drug according to the randomization code provided, yet remain independent of all subject assessments. The pharmacy staff will follow the Standard Operating Procedures and Work Instructions related to pharmacy services and protocol-specific requirements.

Randomization codes will be provided to the unblinded pharmacy staff. Confirmation of receipt of the randomization code will be required by the Sponsor. The unblinded

pharmacy staff will be responsible for maintaining the blind, consistent with protocol design, throughout the study. All documentation is to be filed in the Pharmacy Manual. Access to this manual by study personnel will be restricted to the unblinded pharmacy staff.

The subjects, Principal Investigator, and all other study personnel involved with subject assessments will remain blinded to the actual treatment assignments of the subjects. The Principal Investigator will be ultimately responsible for ensuring that the integrity of the blind is maintained throughout the study, and will be required to notify the Sponsor in the event of any breaking of the blind for any reason.

#### 6.2.1 Clinical Research Staff

All observers who evaluate any reported adverse event, laboratory abnormalities, ECGs, and changes in the ECGs will be blinded as to what treatment sequence each subject is assigned.

#### 6.2.2 Study Subjects

All subjects will be blinded as to which treatment they are receiving at any dose.

#### 6.2.3 Bioanalytical Laboratory

All samples will be sent to the bioanalytical laboratory for analysis. The bioanalytical laboratory will be unblinded and only run the analysis on active treatment subjects.

#### 6.2.4 Pharmacokinetic Analysis

Pharmacokinetic analysis will be completed only on the active treatment subjects and will be blinded by subject for interim assessments.

#### 6.2.5 Unblinding Procedures

As data from each cohort is informative for dose escalation decisions in subsequent cohorts, review of unblinded data will be conducted after completion of each cohort by 2 experienced individuals not directly involved in the study, one of whom must be a physician. Per protocol, the dose escalation meeting and decision require PK data through the morning of Day 15 and approximately 21 days of safety data, depending on the turnaround time of the bioanalysis. Upon completion of the review, they will communicate to the study team modifications, if any, that should be implemented for subsequent cohorts.

The treatment assignment should be unblinded at the clinic only in the case of an emergency, when knowledge of the study drug assignment is absolutely necessary for the clinical management or welfare of the subject. Breaking of the blind at the clinic under any other circumstances will be considered a protocol violation.

The Investigator is strongly encouraged to contact the Sponsor before unblinding the study drug assignment prior to the scheduled assessment of tolerance and safety data. If the blind is broken for any reason, the Investigator must notify the Sponsor within

1 day, and an SAE form must be completed, if appropriate. In addition, the Investigator will record the date and reason for revealing the blinded study drug assignment for that subject in the source documents and appropriate CRF page(s).

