## 3 STUDY DESIGN SUMMARY

This is a partially-blinded, placebo-controlled, randomized multiple ascending dose (MAD) study to be conducted at one study center.

Thirty-six (36) subjects will be enrolled in 3 cohorts with 12 subjects per cohort. Within each cohort, 9 subjects will be assigned to receive active treatment and 3 subjects will receive placebo. Each subject will participate in one dose level.

The first 2 cohorts (food-effect cohorts) will begin dosing of TBI-223 on Day 1 under fasted conditions, followed by a 3 day washout period and then followed by multiple doses of TBI-223 administered after a high-calorie, high-fat meal from Day 4 through Day 17 (total of 14 days). The third cohort (non-food-effect cohort) will begin dosing of TBI-223 on Day 1 and continue through Day 14, all doses administered after a high-calorie, high-fat meal.

Each subject will be administered TBI-223 or matching placebo with corresponding pharmacokinetic measurements. After each dose cohort, the Sponsor and Investigator will review the pharmacokinetic and safety data before proceeding to the next dose level.

Dose escalation to the next cohort (i.e., dose level) or decisions regarding changed or additional cohorts will not take place until the Sponsor, in conjunction with the Principal Investigator and dose escalating committee, has determined that adequate safety, tolerability, and pharmacokinetics from the previous cohort(s) have been demonstrated to permit proceeding to the next cohort. The Institutional Review Board (IRB) should be immediately notified of the dose escalation or any revised approach for review and approval.

Safety will be assessed throughout the study for all subjects. Safety assessments will include physical and detailed neurological examinations, vital signs (blood pressure, pulse rate, respiration rate, temperature and pulse oximetry), ECGs, cardiac monitoring, adverse events (AEs), and clinical laboratory tests (including hematology, serology, serum chemistry, coagulation, and urinalysis).

Blood and urine will be collected for clinical laboratory evaluations.

The Principal Investigator, in conjunction with the Sponsor may collect additional blood if necessary, for repeat laboratory or safety evaluations including AE follow up.

Female subjects will have blood collected for serum pregnancy testing. Females claiming postmenopausal status will have blood collected to measure follicle stimulating hormone (FSH) levels.

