### 3.1 Dose Escalation

#### Dose Escalation Review

The review of all pertinent safety/tolerability data will include physical examinations, ECGs, vital signs, clinical laboratory tests, cardiac monitoring, and adverse events (AEs or SAEs) through Day 30 (non-food-effect cohort) or Day 33 (food-effect cohorts). Data considered will include data from the current dose cohort and all previous cohorts. The Sponsor and Investigator will determine if there is sufficient data available from all participating subjects to make a dose escalation decision.

Any AEs of grade  $\geq 2$  toxicities (per DMID toxicity table; Appendix 3) must be discussed in the determination of escalation to the next dose level. PK analysis will be completed only on the active treatment subjects and will be blinded by subject. ECG

data will be analyzed in a blinded fashion and unblinded by ECG vendor in order to be presented by treatment group in aggregate (reviewers will not be unblinded by subject).

Upon review of relevant cohort data, the Sponsor, in conjunction with the Investigator, may decide to:

1. Escalate the dose as planned.
2. Evaluate an intermediate dose level prior to proceeding to the next planned dose level based on PK and safety data of preceding groups.
3. Repeat a given dose level in a new cohort of subjects.
4. Increase the dose of the next cohort if the PK is lower than expected in the previous cohort.
5. Add a cohort if the PK is lower than expected after a cohort and there are no safety concerns.
6. Halt the study.

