- Day 14: AUCtau, Cmax, Cmin, Ctrough (i.e., C0), C24, Cavg, Tmax, CL/F, Vz/F,  $\lambda_z$ , t1/2, RAUC, RCmax

For the food-effect cohorts, PK parameters calculated from plasma concentration of TBI-223 and M2 following doses on Days 1, 4, and 17 will include, as appropriate:

- Day 1: AUCtau, AUCextrap, AUCinf, Cmax, C24, Clast, Tmax, Tlast, CL/F, Vz/F,  $\lambda_z$ , t1/2.
- Day 4: AUCtau, Cmax, C24, Cavg, Tmax. Additionally, AUCinf, AUCextrap, CL/F, Vz/F,  $\lambda_z$ , t1/2 should be included if AUCtau  $\geq$  70% of AUCinf.
- Day 17: AUCtau, Cmax, Cmin, Ctrough (i.e., C0), C24, Cavg, Tmax, CL/F, Vz/F,  $\lambda_z$ , t1/2, RAUC, RCmax

Each parameter will be estimated separately for each participant using plasma concentrations of TBI-223 and, as appropriate M2.

Each day one blood sample will be taken immediately before dosing, to measure Ctrough level and to observe the time that steady state is achieved.

Assessments of food effect will include geometric mean ratios of Cmax and AUCtau between Day 1 (fasted) and Day 4 (fed), as well as graphical displays of the profiles. Model-based approaches and comparisons with results from the single-dose study, TBI-223-CL-001, may also be undertaken.

Both individual-participant and group summary-statistics (n, mean, median, geometric mean, standard deviation, standard error of the mean, coefficient of variation, minimum, maximum) data will be reported. Summary statistics will be presented by gender. All tests will be performed using a 2-sided  $\alpha$ -level of 0.05, and appropriate confidence intervals will be provided.

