## 13 EVENTS SCHEDULE

**Table 12 Schedule of Assessments (Cohorts 1 and 2)**

	SCREEN	CHECK-IN a	Fasted dosing Day 1 and washout Day 2-3			TREATMENT (14 Days) Day 18-19 Follow-up					CHECK OUT	FOLLOW-UP			EARLY WITHDRAWAL	
			-1	1	2	3	4	5-10	11	12-17		20	21-25	26	33 (+1)	
DAY	-28 to -2	-2														
EVENT																
Informed consent and medical history	X															
Check-in questions		X														
Height, weight	X															
HIV/ hepatitis B, C	X															
Serum pregnancy test b	X	X														
FSH b	X															
Urine drug/alcohol/cotinine screen	X	X														
Safety Labs (hematology, chemistry) c	X		X	X	X	X	X	X c		X c		X		X	X	
Coagulation d	X		X	X		X	X	X d		X d		X		X	X	
Urinalysis e	X		X	X		X	X	X e		X e		X		X		
Physical and neurological exams f	X	X	X	X	X	X	X	X f		X f			X		X	
Vital signs (blood pressure, pulse, temperature, respiration rate, and pulse oximetry) g	X	X		X	X	X	X	X	X	X	X	X	X		X	
Concomitant medication review h			←							→						
Adverse events i			←							→						

Protocol TBI-223 CL-002 Version 1.0

	SCREEN	CHECK-IN a	Fasted dosing Day 1 and washout Day 2-3				TREATMENT (14 Days) Day 18-19 Follow-up				CHECK OUT	FOLLOW-UP			EARLY WITHDRAWAL
			-1	1	2	3	4	5-10	11	12-17		20	21-25	26	33 (+1)
DAY	-28 to -2	-2													
EVENT															
Dose j				X			X	X	X	X					
12-lead safety ECGs k	X	X	X	X			X	X		X	X		X		X
Plasma for predose trough PK l,m				X			X	X	X	X					
Plasma for Postdose PK n				X	X	X	X			X	X	X			

ECG = electrocardiogram; FSH = follicle-stimulating hormone; HIV = human immunodeficiency virus; PK = pharmacokinetic.

- a. Confinement to start at Check-in (evening of Day -2) and continue until 72 hours after dosing on Day 17.
- b. Serum pregnancy test at screening and at check-in for females only. FSH completed for postmenopausal females only.
- c. Blood will be collected for safety labs (hematology and chemistry) at Screening and Day -1 and at 6-7 hours postdose on Days 1, 2, 3, 4, 6, 10, 14, 17, and on Days 20 and 26
- d. Blood for coagulation testing will be collected at Screening and Day -1, and 6-7 hours postdose on Days 1, 3, 4, 6, 10, 14, 17, and on Days 20 and 26.

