- k. 12-lead safety ECGs will be printed and reviewed on-site by the Principal Investigator or designee. Triplicate ECGs will be completed at screening, Day -2, Day -1, and on Day 26 or upon early withdrawal. All other time points will be single ECG readings. ECGs may be done within 2 hours prior

Protocol TBI-223 CL-002 Version 1.0

to time of dosing and at 3, 6, 12 and 16 hours postdose on Days 1, 4, 8, 10, 12, 14, 17, and on Days 18 and 20. Another single ECG reading will be performed on the morning of Day 20 before discharge. The predose ECG should be completed within 20 minutes prior to the predose blood draw. If a subject experiences a post-dosing QTcF >500 msec with a change-from-baseline QTcF >60 msec, after repeat testing, additional ECGs should be recorded until normalization or return to baseline

- l. Predose trough blood samples will be drawn on Day 1 and daily starting on Day 4.
- m. Duplicate plasma samples will be generated from all blood pharmacokinetic samples.
- n. Postdose blood plasma samples will be drawn at the following timepoints:
  - Day 1: 0.5, 1, 2, 3, 4, 5, 6, 7, 8, 12, 16, 20, 24, 30, 36, 42, 48, 54, 60, and 72 hours. The 72-hour sample is the predose sample of Day 4.
  - Day 4: 0.5, 1, 2, 3, 4, 5, 6, 7, 8, 12, 16, 20, and 24 hours. The 24-hour sample is the predose sample of Day 5.
  - Day 17: 0.5, 1, 2, 3, 4, 5, 6, 7, 8, 12, 16, 20, 24, 30, 36, 42, 48, 54, 60, and 72 hours

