- k. 12-lead safety ECGs will be printed and reviewed on-site by the Principal Investigator or designee. Triplicate ECGs will be completed at screening, Day -2, Day -1, and on Day 23 or upon early withdrawal. All other time points will be single ECG readings. ECGs may be done within 2 hours prior to time of dosing and at 3, 6, 12, and 16 hours postdose on Days 1, 2, 3, 8, 12. Another single ECG reading will be performed on the morning of Day 17 before discharge. The predose ECG should be completed within 20 minutes prior to the pre-dose blood draw. If a subject experiences a post-dosing QTcF  $>500$  msec with a change-from-baseline QTcF  $>60$  msec, after repeat testing, additional ECGs should be recorded until normalization or return to baseline
- l. Predose trough blood samples will be drawn daily starting on Day 1.
- m. Duplicate plasma samples will be generated from all blood pharmacokinetic samples.
- n. Postdose blood plasma samples will be drawn at the following timepoints:
  - Day 1: 0.5, 1, 2, 3, 4, 5, 6, 7, 8, 12, 16, 20, and 24 hours. The 24-hour sample is the predose sample of Day 2.
  - Day 14-17: 0.5, 1, 2, 3, 4, 5, 6, 7, 8, 12, 16, 20, 24, 30, 36, 42, 48, 54, 60, and 72 hours

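### The escalation data cut in Section 6.2.5 fits only Cohort 3: in Cohorts 1 and 2, Day 15 precedes the sole steady-state PK profile, and 21 days of safety data falls short of Section 3.1

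*Protocol*

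**What the plan says.** Section 6.2.5 (Unblinding Procedures) provides that "review of unblinded data will be conducted after completion of each cohort". It then states what the escalation meeting and decision need: they "require PK data through the morning of Day 15 and approximately 21 days of safety data, depending on the turnaround time of the bioanalysis". One rule covers all cohorts.

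The cohorts do not share a calendar. Under Section 3, Cohorts 1 and 2 take a single fasted dose on Day 1 and 14 fed doses on Days 4 to 17. Cohort 3 takes 14 fed doses on Days 1 to 14.

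Section 9.2 fixes when PK parameters are derived: "For the food-effect cohorts, PK parameters calculated from plasma concentration of TBI-223 and M2 following doses on Days 1, 4, and 17". Of these three days, only Day 17 follows repeated dosing. Table 12, footnote n, gives its sampling times: "Day 17: 0.5, 1, 2, 3, 4, 5, 6, 7, 8, 12, 16, 20, 24, 30, 36, 42, 48, 54, 60, and 72 hours". In Cohort 3 the corresponding profile starts on Day 14 (Table 13, footnote n).

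Section 3.1 (Dose Escalation) describes the safety data to be reviewed differently, as running "through Day 30 (non-food-effect cohort) or Day 33 (food-effect cohorts". It names no PK cut-off day, so Section 6.2.5 is the only place that sets one.

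**The concern.** The Day 15 cut matches the schedule of the one cohort that precedes no planned escalation. For the steps from Cohort 1 to 2 and from Cohort 2 to 3, the stated requirement can be met with the Day 1 fasted profile, the Day 4 first-fed-dose profile and troughs.

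That matters because the doses were chosen on simulated steady-state Cmax and AUC (Section 1.7, Table 3), while earlier human data are from single doses only (Section 1.5). Section 3.1 lets the sponsor raise a dose or add a cohort when PK is lower than expected, and the expected values are steady-state ones. In Cohorts 1 and 2 the quantities to compare with them (multiple-dose AUCtau and Cmax), together with Cmin, RAUC and RCmax, come only from Day 17.

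Two background facts add weight. The dog nervous-system effects depended on both dose and duration, and it is not known whether Cmax or AUC drives them (Section 1.3). The single-dose concentration-QTc analysis excludes an effect above 10 ms only up to about 8 µg/mL of TBI-223 (Section 1.5). Predicted steady-state Cmax is 7.9 µg/mL in Cohort 2 and 9.7 µg/mL in Cohort 3.

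On safety, Sections 3.1 and 6.2.5 give different amounts of follow-up for the same decision, and 6.2.5 sets the lower bar.

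**Working it through.** **PK cut: day of the 24-hour sample after the last dose = last dose day + 1**

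- Cohort 3: 14 + 1 = Day 15. The protocol's figure is reproduced.
- Cohorts 1 and 2: 17 + 1 = Day 18. It is not reproduced.
- Fed doses given in Cohorts 1 and 2 before the morning of Day 15: Days 4 to 14, so 14 − 4 + 1 = 11 of 14.

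Counting from the first fed dose (Day 4 as relative Day 1), relative Day 15 is study Day 18, which would fit. The protocol defines no such count and uses study days throughout.

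**Samples per subject, Cohorts 1 and 2 (Table 12, footnotes l and n)**

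| Source | Planned | Through morning of Day 15 |
|---|---|---|
| Day 1 postdose (20 less the 72-h sample, which is the Day 4 predose) | 19 | 19 |
| Day 4 postdose (13 less the 24-h sample, which is the Day 5 predose) | 12 | 12 |
| Day 17 postdose | 20 | 0 |
| Troughs (Day 1, then daily from Day 4) | 15 | 13 |
| Total | 66 | 44 |

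The planned column agrees with Table 6: 19 + 12 + 20 = 51 postdose samples and 15 troughs. Not required: 66 − 44 = 22, made up of the 20 Day 17 postdose samples (13 of them at 0.5 to 24 h, within the dosing interval) and the Day 16 and 17 troughs. Of the 13 troughs that are covered, 11 (Days 5 to 15) follow fed dosing. The other two are the pre-drug sample on Day 1 and the 72-hour sample after the fasted dose.

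**Safety cut**

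Section 6.2.5 gives no starting point for the 21 days, so each plausible one is shown (there is no Day 0).

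| Cohorts | Count from | 21st day | Days short of end-of-study visit | Days short of Section 3.1 cut |
|---|---|---|---|---|
| 1 and 2 | Day −2 | 19 | 26 − 19 = 7 | 33 − 19 = 14 |
| 1 and 2 | Day 1 | 21 | 26 − 21 = 5 | 33 − 21 = 12 |
| 1 and 2 | Day 4 | 24 | 26 − 24 = 2 | 33 − 24 = 9 |
| 3 | Day −2 | 19 | 23 − 19 = 4 | 30 − 19 = 11 |
| 3 | Day 1 | 21 | 23 − 21 = 2 | 30 − 21 = 9 |

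No starting point reaches the end-of-study visit or the Section 3.1 day. In Cohorts 1 and 2, safety labs are scheduled "at 6-7 hours postdose on Days 1, 2, 3, 4, 6, 10, 14, 17, and on Days 20 and 26". Counting from Day 1 or Day 4 keeps the Day 20 labs and the Day 18 and 20 ECGs; counting from check-in loses the Day 20 assessments. Neurological examinations through Day 17 are covered on every count. The Day 26 labs, triplicate ECG and neurological examination are covered on none.

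**Margins at the predicted exposures (Section 1.7)**

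- Against the lowest preclinical no-adverse-effect level of 20.2 µg/mL: Cohort 2, 7.9 / 20.2 = 39%; Cohort 3, 9.7 / 20.2 = 48%.
- Against the 8 µg/mL QTc limit: Cohort 2, 7.9 / 8 = 0.99; Cohort 3, 9.7 / 8 = 1.21.

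**The case against.** The strongest reply is that Section 6.2.5 sets a floor, not a cap. The review follows completion of the cohort, by which time the Day 17 to 20 samples have been drawn. Section 3 bars escalation until adequate pharmacokinetics have been shown, and a team that followed Section 3.1 on safety would satisfy both sections. This stands as far as it goes. But drawn is not the same as assayed and reviewed, and neither Section 3 nor Section 3.1 names a PK day that would override Day 15.

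A second reply is that little accumulation is expected, so the Day 4 profile should be close to the Day 17 one. The single-dose results support this. Scaling the 2000 mg fed IR means by the SR-1 ratios gives, at 1800 mg, AUC 100 × 0.7045 × 0.9 = 63.4 µg·h/mL and Cmax 19.7 × 0.3539 × 0.9 = 6.3 µg/mL. Table 3 predicts 63.8 and 5.7 at steady state. (The scaling is approximate, because it applies geometric ratios to arithmetic means.) The 11 troughs after fed doses would show marked unexpected accumulation. Single doses have also reached mean Cmax of 16.2 to 19.7 µg/mL and, at 2600 mg, a mean AUC of 127 µg·h/mL, above Cohort 3's predicted 115.2, and were described as well tolerated. These points lower the risk. They do not replace the Day 17 profile: negligible accumulation is itself a prediction from single-dose data, and troughs give neither Cmax nor AUC.

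Third, the substantive safety gap is one visit, because Days 27 to 33 hold only a phone call. That is right, and it limits the size of the safety part.

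**Conclusion.** The point holds and should be fixed. As written, both planned escalations could meet the Section 6.2.5 requirement without any steady-state AUCtau, Cmax, Cmin or accumulation ratio from the preceding cohort: 22 of 66 PK samples per subject, including the whole Day 17 profile, fall outside it. The safety requirement is 9 to 14 days shorter than Section 3.1's in Cohorts 1 and 2 and 9 to 11 days shorter in Cohort 3. The words allowing for approximation and assay turnaround do not span that gap.

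The consequence is moderate. Reviewers would still hold full fasted and fed single-dose profiles and the troughs, predicted Cmax stays below half the preclinical no-adverse-effect level, and the safety shortfall is essentially the end-of-study visit.

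The conclusion assumes that Day 15 means study Day 15, as days are numbered everywhere else in the protocol. If it was meant as the 15th day from the first fed dose, the PK mismatch disappears, but the text needs to say so and the safety conflict remains. The start of the 21 days is unknown, hence the ranges. Assay turnaround is not stated either, so how often the Day 17 results would be available anyway cannot be judged from the protocol.

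**What to change.** In Section 6.2.5, replace the single Day 15 cut with PK through at least 24 hours after the last dose: the morning of Day 18 in Cohorts 1 and 2, the morning of Day 15 in Cohort 3, and the equivalent day for any added cohort. Replace the 21-day safety requirement with a reference to Section 3.1 (Day 33 for food-effect cohorts, Day 30 for the non-food-effect cohort), so that the cut is stated in one place. If the sponsor prefers a shorter safety cut, Section 3.1 should be changed to match, and the cut should not precede the end-of-study visit.

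This is a change of wording with no added procedures or blood draws. In Cohorts 1 and 2 the PK cut moves by 18 − 15 = 3 days, which need not delay a meeting already held after cohort completion. It brings 13 Day 17 samples and 2 troughs into the required set: 15 × 9 active subjects = 135 already-planned samples per cohort to be assayed before the meeting. The safety wait is the one Section 3.1 already implies.
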